Development and internal validation of models involving vital signs to predict troponin level and myocardial injury after noncardiac surgery: a single-centre retrospective cohort study

Introduction

The incidence of myocardial injury after noncardiac surgery (MINS) is approximately 12-15% and is associated with an increased risk of 30-day mortality (1), 1-year mortality (2), and 2-year major vascular events (3). Since more than 90% of patients with MINS are asymptomatic, routine troponin monitoring is required for detection (4). The postoperative days 0, 1, and 2 accounts for approximately 40%, 40%, and 10% of MINS, respectively (4). Presently, the Canadian Cardiovascular Society (CCS) perioperative guidelines recommend patients identified to be at risk according to the Revised Cardiac Risk Index (RCRI) and BNP/NT-proB-type Natriuretic Peptide (NT-proBNP) receive daily postoperative troponin monitoring for three days to identify MINS events (5). European and American societies have similar recommendations for troponin monitoring to detect MINS (6).

Current risk stratification models have multiple limitations (4). Most importantly, they predict an elevated risk over the postoperative period but cannot pinpoint when MINS may happen in the postoperative course given the patients' changing condition. Moreover, prescription of troponin monitoring is not universal (7), infrequent and inconsistent troponin monitoring may lead to delayed detection and management, and the rise of troponin is delayed by 3-4 hours from the time of injury (4).

Retrospective cohort studies show association amongst intraoperative and postoperative derangements in vital signs and MINS (4). Vital signs are routinely available within the electronic medical record, and may serve as objective predictors (i.e. as opposed to free text and disease names that have higher risks of misclassification and errors). Using both traditional longitudinal analysis techniques and novel methods in machine learning, we will investigate whether intraoperative and postoperative vital signs can enhance MINS surveillance by providing temporal prediction of MINS events.

Table 1. Preoperative factors studied in literature associated with MINS and/or major myocardial complication and mortality

Variable	References
Age	Goldman 1977 (8), Lee 1999 (9), Kheterpal 2009 (10), Botto 2014 (11), House 2016 (12)
Congestive heart failure	Lee 1999, Botto 2014
Coronary artery disease	Lee 1999, Kheterpal 2009, Botto 2014
Cerebrovascular disease	Lee 1999, Kheterpal 2009, Botto 2014

Peripheral vascular disease	Botto 2014
Diabetes	Lee 1999 (Insulin-dependent), Botto 2014 (though not found to be predictive in Kheterpal 2009)
RCRI	Lee 1999
Hypertension	Kheterpal 2009 (hypertension requiring medication), Botto 2014, Ruetzler 2020 (4)
Kidney function (laboratory)	Lee 1999, Botto 2014 (though not found to be predictive in Kheterpal 2009)
BNP / NT-proBNP	Choi 2010 (13), Rodseth 2013 (14) and 2014 (15) metanalyses, Malhotra 2016 (16), Duceppe 2020 (17)
Anemia	Feng 2017 (18)
Heart rate	Abbott 2016 (>96) (19), Laitio 2004 (increased variability) (20), Devereaux 2011 (every increase by 10 from baseline) (21)
American Society of Anesthesiologist physical status	House 2016

Table 2. Intraoperative factors studied in literature associated with MINS and/or major myocardial complication and mortality

Variable	References
Type and risk of surgery (various definitions)	Lee 1999, Boersma 2005 (22), Davenport 2007 (23) Not found to be predictive in Kheterpal 2009 likely due to different definitions and study populations.
Emergency surgery	Detsky 1986 (24), Boersma 2005, Kheterpal 2009, Botto 2014, House 2016, Zhao 2017 (25), House 2016 Emergency surgery patients excluded in RCRI (Lee 1999)
Red blood cell (RBC) transfusion	Kheterpal 2009, Whitlock 2015 (26), Wu 2010 (27), Glance 2011 (28), Devereaux 2011

Hypotension (mmHg)	Wesselink 2018 (29), Sessler 2018 (30)
Tachycardia (beats)	House 2016 (>100 beats for >59 minutes), Abbott 2018 (>100)

Table 3. Postoperative factors studied in literature associated with MINS and/or major myocardial complication and mortality

Variable	References
Postoperative hypotension	van Lier 2018 (quartiles, 3 days postoperatively) (31), Sessler 2018 (<90mmHg, 4 days postoperatively) Liem 2020 (duration MAP <75, 24 hours postoperatively) (32)
Acute kidney injury	Zhao 2017
Vasopressor use 24 hours after surgery	Zhao 2017

Objectives

1. To develop and internally validate a model that uses the duration and degree of intraoperative and postoperative hypotension to predict the daily maximum troponin level from postoperative days zero to two, in a high risk population where troponin monitoring was ordered.
2. To develop and internally validate a model that uses the duration and degree of intraoperative and postoperative hypotension to predict daily probability of MINS or death (binary outcome, according to the 2021 American Heart Association (AHA) definitions (6) from postoperative days zero to two.
3. To evaluate how different definitions of hypotension affect the primary and secondary models above, and analyze the intraoperative and postoperative hypotension separately to determine whether intraoperative or postoperative hypotension alone are sufficient for prediction.
4. To explore whether other intraoperative and postoperative vital sign information (heart rate, oxygen saturation, and end-tidal carbon dioxide derangements at various definitions) add predictive value to the primary and secondary models above.
5. To use machine learning methods to perform exploratory analysis to determine 1) optimal methods for imputation for time series data; 2) visualization of time series data in the setting of prediction; 3) development and internal validation of machine learning models to use the time series data to predict troponin levels; and 4) to determine how many hours earlier than a binary MINS diagnosis were vital signs able

to predict a MINS diagnosis (as determined by when in the time series prior to MINS diagnosis that the model achieved various thresholds of predicted probability).

Methods

This is a single-center, retrospective cohort study on the development and internal validation of a prediction model.

Population

This study will include patients aged 45 years and older undergoing inpatient noncardiac surgery, who had MINS protocol ordered for postoperative high sensitivity troponin monitoring based on the CCS guidelines (5) from January 2020 to June 2021 (estimated sample size of 750, event rate of ~75).

Patients will be excluded if they do not have intraoperative and postoperative vital signs, or any postoperative troponin measurements. Patients who underwent repeat surgery or were readmitted within the first 72 hours postoperatively will be excluded, since patients who are discharged and readmitted will not have vital measurements as outpatients. If a patient had multiple admissions where the MINS protocol was ordered, only the first inpatient admission will be included. Patients who had positive troponin on postoperative day 4 will be excluded, since vital signs are only included up to postoperative day 3 for consistency.

Data sources

Following research ethics board approval, data will be extracted from Cerner Surginet Anesthesia (intraoperative electronic records) and Cerner PowerChart (preoperative and postoperative electronic records). The extracted data will consist of cohort characteristics (patient, anesthetic, surgical variables relevant to MINS (see Data Dictionary below), and patient vital signs with time stamps up to postoperative day 3. The time series time stamps will be transposed to have the start of surgery as 00:00, Jan 1, 2020. A manual chart review will also be performed to extract data not automatically retrieved from Cerner and Surginet (e.g. diagnoses of morbidities). We will extract relevant preoperative comorbidities, including RCRI and Charlson Comorbidity Index categories that are available to the Cerner team via CIHI with no date limit to obtain all preoperative comorbidities (please see Appendix). The Cerner, Surginet, and chart review data will then be linked by de-identified study ID and full surgery date.

Duration of data collection

Preoperative laboratory values are collected within 30 days before surgery. Preoperative vitals are collected within 24 hours before surgery. The total duration of subsequent data collection will be from the time of surgery up to postoperative day 3 (since the MINS protocol monitors for 3 days) or hospital discharge or death, whichever occurs first. Since 90% of MINS happen between postoperative days zero and two (4) and the frequency of monitoring would likely decrease by postoperative day 3, we will model troponin from postoperative day 0 to postoperative day 2 for the primary analysis to balance utility of the temporal model and prediction data quality.

Outcome

In the primary model, we will model high-sensitivity troponin (hsTnT) level as a continuous outcome, such that the model will remain useful if the troponin threshold definitions for MINS evolve.

In the secondary model, we will use the American Heart Association (AHA) definitions (6) for MINS, briefly:

1. Postoperative hsTnT 20 to <65 ng/L with an absolute increase of ≥ 5 ng/L amongst any postoperative troponins, or ≥ 65 ng/L, “attributable to a presumed ischemic mechanism (ie, supply-demand mismatch or atherothrombosis) in the absence of an overt precipitating nonischemic cause (eg, pulmonary embolism)”. The timestamp for laboratory diagnosis will be set at the time that the sample of elevated troponin was drawn.
 - a. Nonischemic causes that may be temporally associated (around the time prior to troponin elevation) were individually chart reviewed, and include PE/DVT, sepsis, rapid atrial fibrillation, cardioversion within 24 hours as per the VISION trial (33). Rapid atrial fibrillation will be established as the presence of atrial fibrillation on ECG with a ventricular rate >100 bpm. Sepsis will be defined as the presence of infection and a systemic inflammatory response (SIRS) and per the Third International Consensus Definitions for Sepsis and Septic Shock (Sepsis-3). SIRS requires 2 or more of the following features: core temperature > 38 C or < 36 C; heart rate > 90 beats per minute; respiratory rate > 20 breaths per minute; WBC count $> 12 \times 10^9/L$ or $< 4 \times 10^9/L$ (34).
2. In patients with abnormal baseline troponin values (>14 ng/L) that is considered chronic and stable, postoperative myocardial injury is considered acute if there is postoperatively a $\geq 20\%$ rise in high-sensitivity cTnT, or an absolute increase in high-sensitivity cTnT of ≥ 14 ng/L above preoperative values. If a patient was diagnosed as having preoperative acute myocardial infarction, there must be a decrease in preoperative hsTnT to be considered chronic elevation for this rule to apply. Manual physician adjudication will be performed as a double check.

Note that MINS includes myocardial infarction in the AHA definitions. If a patient died before MINS diagnosis within 3 days postoperatively, this will be considered an event - i.e. the outcome is specifically MINS or death, to avoid competing risk bias due to death. However, we anticipate death within 3 days after surgery to be very rare.

Only the first positive MINS event is included, and hemodynamic data will be truncated up to that point. The MINS “diagnosis time” of MINS vs. no MINS is the first troponin in the serial troponin that fits the MINS criteria, with the start time defined as since the start of the surgery.

The exploratory modeling objectives will model both troponin level and MINS definitions.

Vital sign candidate features (predictors)

- Vital signs time series (SBP, MAP, DBP, HR, SpO2): taken from Surginet (intraoperative) and Cerner (preoperatively on the day of surgery, and postoperative)
 - These will be modeled using time series data from 1) intraoperative only, 2) postoperative only, and 3) both intraoperative and postoperative periods, using the following approaches:

- Summary predictor variables as defined by clinicians based on literature (e.g. duration MAP<75, duration HR >100) - different thresholds will be explored
 - **For the primary model, duration MAP<75 will be used (Liem et al.)**
 - Since vitals on the surgical ward may not be measured as frequently, episodes will be defined with the first low value as the start of the event and the first next measurement that is normal as the end of the event.
- Univariate time series (machine learning)
- Multivariate time series (machine learning)

Table 4. Examples of summary variables for vital signs.

These will be modeled based on time stamps as: 1) intraoperative only, 2) postoperative only, and 3) both intraoperative and postoperative periods

Blood pressure	
SBP
 
 1. Maximum decrease from preoperative (defined as median past 24h throughout this table) SBP, as a) absolute change (mmHg), and b) relative change (%) 2. Cumulative duration (minutes) 20% below preoperative preoperative SBP 3. Longest single episode (minutes) below a) 80, b) 90, and c)100 mmHg 4. Cumulative duration (minutes) below a) 80, b) 90, and c)100 mmHg 
MAP
 
 1. Maximum decrease from preoperative MAP, as a) absolute change (mmHg), and b) relative change (%) 2. Cumulative duration (minutes) 20% below preoperative MAP 3. Longest single episode (minutes) below a) 60, b) 65, c) 70, d) 75, e) 80, and f) 85mmHg 4. Cumulative duration (minutes) below a) 50, b) 60, c) 65, d) 70, e) 75, f) 80, and g) 85mmHg
-----------------------	--

Heart rate	
 1. Maximum decrease from preoperative heart rate, as a) absolute change (beats per minute, BPM), and b) relative change (%) 2. Maximum increase from preoperative heart rate, as a) absolute change (BPM), and b) relative change (%) 3. Maximum pulse variation (maximum heart rate minus minimum heart rate) 4. Longest single episode (minutes) below 40, 50, or 60, and above 100, 110, or 120 BPM 5. Cumulative duration (minutes) a) below 60, and b) above 100BPM
Oxygen saturation by pulse oximetry: SpO₂	
 1. Longest single episode (minutes) below a) 88, and b) 90% 2. Cumulative duration (minutes) below a) 88, and b) 90% 3. New postoperative requirement for supplementary oxygen

Other candidate features

For generalizability and to decrease bias, we will select features that are routinely collected. Non-vital sign candidate features include age, sex, urgent/emergent procedure (for the index surgery), postoperative GFR, and comorbidities within the RCRI categories.

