The primary analysis will involve building a linear mixed effects model (with random intercepts) to predict the maximum daily troponin level between postoperative days 0 to 2 as the continuous outcome. The postoperative days 0, 1, and 2 accounts for approximately 40%, 40%, and 10% of MINS, respectively (4). Due to the limitations in retrospective data and the daily troponin monitoring, we will use day as a unit for time rather than hour to avoid overestimation of precision by readers.

For the primary and secondary models described in Objectives 1 and 2, an *a priori* list of predictors will be used: duration hypotension (summarized as a percentage of duration of MAP<75 mmHg in the duration of time modeled, e.g. postoperative day 1) age, sex, emergency surgery, RCRI, and postoperative GFR, as well as the postoperative day and the interaction between postoperative day and % duration MAP<75 mmHg as detailed below.

For longitudinal modeling, the vital signs data and troponin data will be aggregated to the day level, so that the model can predict at the daily temporal level. If there are multiple troponin measurements on the same day, the maximum will be taken. This aggregation of the data is necessary to account for the fact that the vital signs and troponin measurements are measured at irregular intervals (both across patients and data types), often due to the acting physician's response to the patient's condition. Additionally, due to this characteristic of the raw data, the vital signs predictors will be created such that they are standardized to be robust to the number of daily measurements performed (for example, by taking the percentage of day duration, NOT the total duration, of blood pressure below a specific threshold across all measurements during that day). A categorical time variable (representing the day of the measurement) will be included as a predictor within the model.

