Due to the longitudinal nature of the data, we need to include random effects to adjust for the dependence between within-patient daily observations. Thus, at minimum, we intend to include a random intercept corresponding to each patient within the model. However, we may consider including random slopes based on what is observed in the exploratory analysis of the vital signs data, though this would be limited by sample size. Since the effect of a vital signs covariate may be different depending on the day of monitoring, we will investigate interactions between the time predictor and vital signs predictors. This will be performed for only a small number of key time-varying predictors to avoid overfitting, given that the total

number of terms within the model will increase by at least 3 (if the interacting vital signs predictor is continuous or binary) for each additional interaction term included.

Visualizations of the effect of each predictor on the response will also be generated, to further investigate their relationships within the context of the model.

To summarize, a simplified example of the primary linear mixed effects model would be: $\text{Troponin} = \text{intercept} + b1\text{BP_day0} + b2\text{day1} + b3\text{day2} + b4\text{BP_day1*day1} + b5\text{BP_day2*day2} + \text{error}$ (plus other non-BP fixed-effect covariates as listed above). An example interpretation would be $b1$ will correspond to the effect of BP on Day 0, $b4$ will correspond to the additional effect of BP on Day 1 (with respect to Day 0) and $b5$ will correspond to the additional effect of BP on Day 2 (with respect to Day 0). However, we will perform exploratory analysis to explore other forms of longitudinal modeling to select the best model based on discrimination and calibration.

Survival analysis will not be employed due to the small variance in the days for the outcome (days 0-2). Also, right censoring is assumed in survival analysis, which does not apply in our case of troponin rise postoperatively as the majority of patients will not have a troponin increase eventually.

Secondary, Sensitivity, and Exploratory Analyses

In addition to the above outlined primary statistical analysis, we intend to conduct additional secondary, sensitivity and exploratory analyses to address Objectives 2 to 4 to examine how well the model performs given the following changes:

- Introduction of transformations or natural cubic splines on continuous predictors or outcomes

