- Modelling using a generalized linear mixed effects model for binary definitions of troponin increase (per AHA, as described above).
 - Different truncations of vital sign data stream prior to MINS diagnosis (e.g. no truncation, 12h before diagnosis)
 - If sample size allows: subgroup analysis involving only patients with preoperative troponin; subgroup analysis for patients who are in the intensive care unit perioperatively, as this represents a sicker population.
- Intraoperative only, postoperative only
- Further inclusion of additional predictors (e.g. % duration of $\text{HR} > 100$) from the available vital signs data
- Exploration of the incremental value of vital signs in addition to the RCRI or NT-proBNP in predicting MINS or myocardial injury
- Inclusion of information from postoperative day 3
- Delta troponin (change from preoperative troponin) using linear contrast

Model evaluation

To validate the performance of the linear mixed effects model specified in the primary statistical analysis plan, given the longitudinal nature of the data, a repeated patient-based 5-fold cross-validation will be performed with 100 repetitions (doi:

10.1093/gigascience/gix019). Patient-based record was chosen as record-wise cross validation tends to overestimate prediction accuracy compared to subject-wise cross validation. Note that when using a linear mixed effects model to predict troponin for “new”

patients (such as those in a held-out validation set), there are no unique random effects corresponding to those patients and so we are assuming the mean response for these “new” patients. A “patient-based” approach for the cross-validation approach is performed to avoid data leakage from the training set into the validation set (i.e. a patient’s measurements could potentially be present in both the training and validation sets). To quantify predictive performance, the root mean square error (RMSE) will be computed for each repetition, and the corresponding average and standard deviation of those performance measures will be reported. Marginal (i.e. fixed effects only) and conditional (i.e. fixed and random effects) R-squared (Nakagawa and Schielzeth R-squared, doi.org/10.1111/j.2041-210x.2012.00261.x) will be calculated. For assessment of calibration, the predicted values will be averaged across all repetitions (for each actual observation), and a calibration plot will be generated along with measures of the calibration intercept and slope.

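### Objective 3 does not define sufficiency and names no same-covariate model without hypotension, so similar performance of one-period and two-period models would not show that either period predicts

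*Combined protocol and SAP*

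**What the plan says.** Objectives, item 3, sets out to "analyze the intraoperative and postoperative hypotension separately to determine whether intraoperative or postoperative hypotension alone are sufficient for prediction". The method is in Secondary, Sensitivity, and Exploratory Analyses. That section lists variations on the model "to examine how well the model performs given the following changes", and the relevant bullet reads only "Intraoperative only, postoperative only".

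Vital sign candidate features gives three period sets: "1) intraoperative only, 2) postoperative only, and 3) both intraoperative and postoperative periods". There is no set with neither period. Primary Modeling puts the same other predictors in every model, namely "age, sex, emergency surgery, RCRI, and postoperative GFR", plus postoperative day.

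Model evaluation summarises each model separately. For troponin, "the root mean square error (RMSE) will be computed for each repetition", with its average and standard deviation; R-squared and calibration are added. For MINS, a distribution of AUCs over repetitions is formed. No margin, paired difference or interval between models is stated.

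One related analysis exists. A separate bullet proposes exploring what vital signs add to RCRI or NT-proBNP for MINS or myocardial injury.

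**The concern.** Saying that one period alone is sufficient is a claim of two parts: hypotension in that period predicts, and leaving out the other period loses little. The planned fits speak only to the second part. Because every model carries the same covariates, one-period and two-period models can perform alike either because one period carries all the signal or because neither carries any.

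Reading sufficiency as acceptable absolute performance does not help, since the covariates may supply that performance unaided.

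At stake is a numbered objective. The study could report that monitoring one period is enough when its data show only that hypotension adds nothing to the clinical covariates.

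**Working it through.** **Inputs from the documents.** 750 patients and about 75 events (75/750 = 10%); 5-fold patient-based cross-validation with 100 repetitions; three period sets; five shared covariates plus day. The plan gives no margin, threshold or power for Objective 3, so there is no figure of its own to reproduce.

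**Logic.** Let P0, PI, PP and PB be the performance of models with no hypotension term, intraoperative only, postoperative only, and both. The plan yields PI, PP and PB. Two opposite situations give the same planned contrast:

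- neither period predicts: P0 = PI = PB, so PB − PI = 0;
- intraoperative alone suffices: P0 < PI = PB, so PB − PI = 0.

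Only P0 separates them, and Objective 3 does not call for it. The standard deviation over repetitions does not help either: it describes re-splitting of one dataset, not sampling uncertainty in a difference between models.

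**Simulation (all effects assumed).** 750 patients, 10% events, one record per patient, three covariates, standard-normal hypotension scores for the two periods with correlation 0.3 (0.7 in the last row), entered as two separate terms; logistic fits, 5-fold cross-validation with 4 repetitions, 300 datasets per row. Odds ratios are per SD. Monte Carlo standard error is at most √(0.25/300) ≈ 3 points. A match means an AUC no lower than the two-period AUC minus a tolerance of 0 / 0.01 / 0.02.

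| Truth | Mean AUC: none / intra / post / both | At least one single period matches both | Covariates only matches both |
|---|---|---|---|
| No effect | 0.667 / 0.665 / 0.664 / 0.662 | 95 / 99 / 100% | 79 / 94 / 98% |
| Intra only, OR 1.5 | 0.669 / 0.697 / 0.668 / 0.694 | 81 / 98 / 100% | 10 / 25 / 41% |
| Post only, OR 1.5 | 0.665 / 0.665 / 0.691 / 0.688 | 82 / 98 / 100% | 11 / 31 / 53% |
| Both, OR 1.3 | 0.665 / 0.682 / 0.685 / 0.691 | 54 / 95 / 100% | 8 / 20 / 41% |
| Both, OR 1.5 | 0.663 / 0.706 / 0.707 / 0.725 | 18 / 60 / 93% | 0 / 1 / 4% |
| Both, OR 1.3, correlation 0.7 | 0.669 / 0.700 / 0.701 / 0.703 | 82 / 100 / 100% | 3 / 12 / 25% |

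The third column hardly separates the first three rows; the fourth does. For a named period, the intraoperative-only model matches at zero tolerance in 82% of datasets with no effect and 80% when it truly suffices.

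**Sensitivity to coding (zero tolerance).** The plan does not say whether the both-period model has one pooled hypotension variable or two.

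- Pooled: at least one period matched in 73% and 84% of datasets with no effect (two runs), against 84-85% and 77-80% respectively when one period truly sufficed.
- Two terms: 95-98% with no effect, against 74-86%.
- Covariates only matched or beat both periods in 79-86% with no effect, against 10-34% when one period predicted.

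**RMSE.** In a separate two-term simulation with three days per patient (150 datasets per scenario), at least one period matched on RMSE in 99% with no effect, but in 3% and 0% when both periods contributed.

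**Effect of a reference model.** In the tabulated simulation at tolerance 0.01, also requiring a single-period model to beat covariates only by more than 0.01 AUC cut false sufficiency with no effect from 99% to 8%. It kept 81% and 76% when one period truly sufficed. It still passed one period in 79% (OR 1.3) and 60% (OR 1.5) when both mattered, so the loss needs its own interval and margin.

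**The case against.** The plan states no decision rule. A reader might infer that a period will be called sufficient whenever its model does as well as the two-period model, but no section says so; judging a one-period model on its own AUC and calibration is equally natural. This stands, and the match rates above describe one possible reading. The gap remains under the other reading, because covariates alone reached an AUC of 0.667 in the no-effect row, against 0.665 and 0.664 with one period added.

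A reader might also infer that a match arises most often when hypotension predicts nothing. The results do not support that: at tolerance 0.01 the rates are 99% and 98%, and under pooled coding the ordering changed between runs. Nor can one say that cross-validation penalises the two-period model for extra terms, since the plan defines hypotension as a single percentage of the time modelled.

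The plan has partial safeguards. The incremental-value bullet tests vital signs, but on an RCRI or NT-proBNP base, for MINS or myocardial injury, and without a link to Objective 3; it gives no cover for troponin level. The coefficients and effect plots would help an attentive reader. Marginal R-squared covers all fixed effects together, and the decision curves compare with ordering troponin for everyone or no one. None of these is tied to the sufficiency question.

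Finally, these are secondary or exploratory analyses in a single-centre study, which limits the weight of the point but does not make the answer interpretable.

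**Conclusion.** The concern holds in this form: Objective 3 promises a determination that the planned comparison cannot deliver, because sufficiency is undefined, the hypotension-free reference is missing, and no uncertainty is attached to differences between models. This follows from the text and needs no simulation.

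The size is indicative only. With no effect, at least one single-period model matched the two-period AUC in about 73-98% of datasets depending on coding, and similar rates arose when one period truly sufficed. The no-signal ambiguity affects both outcomes. Overlooking a real second-period contribution is essentially an AUC problem. Effect sizes, covariate strengths, correlations and coding are assumptions; the documents give none, and the simulations simplify the mixed models. The primary model under Objective 1 is unaffected.

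**What to change.** For both the troponin and the MINS models:

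1. Add a reference fit with the same covariates and day but no hypotension terms, on the same patients and folds.
2. State how the both-period hypotension variable is built.
3. Report paired patient-level bootstrap intervals for (a) the gain in RMSE or AUC of the both-period and each single-period model over the reference, and (b) the loss from dropping each period.
4. Call a period sufficient only if there is a gain over the reference and the loss lies within a margin the sponsor fixes in advance. Otherwise report no hypotension signal, or inconclusive, as applies.

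The cost is a few lines in the plan, one extra fit per outcome and a bootstrap; no new data are needed. The reference has fewer terms than the planned models, so it does not strain the parameter limits. The downside is that, with about 75 events, the binary model will often be inconclusive. The rates above come from a point-estimate version of the rule; the interval version was not simulated.
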